**10.2 SECONDARY OBJECTIVE**

The secondary objective of the study is to evaluate the performance of CSGS, defined here as the feasibility to measure electrophysiological properties of the occlusion in vivo during EVT procedures for the treatment of acute ischemic stroke.

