### 11.2 SECONDARY ENDPOINTS

The Secondary Endpoints are:

1. The concordance between aggregated occlusion measurements (**clot scale**) done by CSGS, and the histopathology results of the clot retrieved during the EVT procedure, regarding **red blood cell content** in the occlusion.
2. The ability of CSGS detecting the **proximal end of the occlusion** (sensor-scale), as compared to the physician's labelling (tag 'PRE-CLOT' for no occlusion contact and tag 'CLOT' for occlusion contact).
3. **Procedural success** defined as the ability to navigate CSGS to the occlusion site and measure electrophysiological properties of the occlusion.
4. The ability to perform binary classification of individual electrophysiological parameter measurements (**local scale**) by distinguishing local regions with substantial platelet content (**platelet-positive**) from regions with negligible platelet content (**platelet-negative**) in the occlusion.
5. The concordance between aggregated occlusion measurements (**clot scale**) done by CSGS, and the histopathology results of the clot retrieved during the EVT procedure, regarding **platelet content** in the occlusion.
6. The ability to perform binary classification of individual electrophysiological parameter measurements (**local scale**) by distinguishing local regions with substantial fibrin content (**fibrin-positive**) from regions with negligible fibrin content (**fibrin-negative**) in the occlusion.

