**13.8 STUDY PROCEDURE**

Clotild® guidewire will be inserted and up to 6 measurements will be done: 1 measurement distal to the access catheter in circulating blood (this is the reference measurement), 1 measurement proximal to the site of occlusion, 2 to 3 measurements inside the occlusion and 1 measurement at the most distal advancement of the guidewire (ideally distal to the occlusion). Each of these measurements will be tagged using the tablet interface.

Note that the study procedure includes the manipulation of the CSGS, from the tablet preparation to removal of the study device from the sheath, and not the clot removal.

\*Study Procedure: preparation tablet till removal study device from sheath

*Figure 7: Schematic explaining how the study procedure is structured within the EVT.*

During the study procedure the CSGS may be used to navigate other devices involved in the EVT, taking the CSGS IFU into consideration.

Procedural success is defined as the ability to navigate CSGS to the occlusion site and measure electrophysiological properties of the occlusion.

A Treated patient is a patient in whom the CSGS went through the introduction sheath.

The occlusion material recovered during the EVT procedure will be immediately stored in a preservative solution of formaldehyde (refer to section 14.1) and sent to the histo-pathology lab for preparation. Analysis of histo-pathology of the occlusion will be conducted in a core central laboratory. Correlation with the electrophysiological properties will be done by the SENSOME data team.

During the procedure, the following data will be collected:

- Digital Subtraction Angiography images
- Vascular perforation, dissection, or device failure.

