**Clinical investigation plan - CLOT OUT****15.2 ANALYSES POPULATION**

This study will be conducted in subjects presenting an acute ischemic stroke due to M1 occlusion, eligible for EVT based on neuro-interventionist and/or neurologist investigators' opinion.

Intention To Treat (ITT) Population

All patients who were enrolled, so all patients (or legally authorized representatives) who signed and dated the patient information consent form even though the CSGS was not used in the subject.

The **safety analysis** (amount of AE) will be performed on the intention to treat (ITT) population.

Treated Population

All patients in which the guidewire went through the sheath, even though if not all eligibility criteria were met or if a device failure occurred or if the clot could not be retrieved.

The **primary safety endpoint** will be determined on the Treated Population.

Per-protocol Population

All patients from the Treated Population who comply to all eligibility criteria.

No separate analyses will be performed for the per-protocol population.

Development Performance Population

This population includes patients from whom at least 1 evaluable acquisition was captured by the CSGS. An evaluable acquisition is defined as a "CLOT tag" or "Clot or beyond" tag with non-anomalous (see criteria section 15.6) impedance measurement. Data of this population will be used during the development phase to build the different models for classification of RBC-positive and platelet-positive.

Local-Scale Performance Population

This population includes patients for whom non-anomalous acquisition was collected by the CSGS during at least one tagged measurement with clot contact excluding patients from the Development Performance Population. Data of this population will be used during the validation phase to validate the model built during the development phase.

The analysis of the **primary performance endpoint** will be performed on data from the Local-Scale Performance Population.

Clot-Scale Performance Population

All patients from the Local-Scale Performance Population of which the clot could be retrieved for histological assessment.

Performance evaluation of the secondary performance endpoints related to the clot scale will be done on the Clot-Scale Performance Population.

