**Clinical investigation plan - CLOT OUT**

- at most one missing or anomalous individual measurement (see identification of anomalous measurements in 15.6).
3. Procedural success defined as the ability to navigate CSGS to the occlusion and measure electrophysiological properties of the occlusion. Procedural success is achieved from the moment that at least 1 evaluable measurement is captured by the CSGS.
  4. The ability to perform binary classification of individual electrophysiological parameter measurements (local scale) by distinguishing local regions with substantial platelet content (platelet-positive) from regions with negligible platelet content (platelet-negative) in the occlusion.
    - The ability to perform binary classification will be evaluated by the performance metric Area Under the Receiver Operator Characteristic curve (AUC of ROC) computed from the platelet-content score predicted on the validation dataset. The same methodology will be used as for the primary performance endpoint.
  5. The concordance between aggregated occlusion measurements (clot scale) done by CSGS, and the histopathology results of the clot retrieved during the EVT procedure, regarding platelet content in the occlusion.
    - To determine the histopathological results of the clot, the platelet composition (value between 0 and 1) will be averaged over the 3 analyzed slides provided by the Core Laboratory.
    - Significant correlation will be judged at the 0.05 significance level by the t-statistic of the relation between platelet content as output by the prediction model and the platelet as quantified by the CD42b immunochemistry staining histological analysis.
  6. The ability to perform binary classification of individual electrophysiological parameter measurements (local scale) by distinguishing local regions with substantial fibrin content (fibrin-positive) from regions with negligible fibrin content (fibrin-negative) in the occlusion.
    - The ability to perform binary classification will be evaluated by the performance metric AUC of ROC computed from the fibrin-content score predicted on the validation dataset. The same methodology will be used as for the primary performance endpoint.
  7. The concordance between aggregated occlusion measurements (clot scale) done by CSGS, and the histopathology results of the clot retrieved during the EVT procedure, regarding fibrin content in the occlusion.

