## 2. Study objective

The objective of the study is to evaluate the safety and the possibility of Clotild® Smart Guidewire System (CSGS) to provide electrophysiological measurements. The electrophysiological measurements will be used to update CSGS's database and thus improve the prediction accuracy of the model in providing physicians with insights for mechanical thrombectomy.

The **primary objective** of the study is to evaluate the **safety** of using Clotild® Smart Guidewire System (CSGS) at the occlusion location during an EndoVascular Thrombectomy (EVT) procedure for the treatment of subjects with acute ischemic stroke eligible for EVT.

Safety will be evaluated by means of the amount of intracranial vessel perforations and/or dissections with the CSGS during the procedure.

The **secondary objective** of the study is to evaluate the **performance** of CSGS, defined here as the feasibility to measure electrophysiological properties of the occlusion in vivo during EVT procedures for the treatment of acute ischemic stroke.

Performance will be evaluated by the ability to correctly binary classify the clot as Red Blood Cell (RBC) positive or RBC negative, platelet positive or negative and fibrin positive or negative. Performance endpoints that focus on clot characterization are split in two categories: one category that demonstrates the ability of an automatic system to correctly identify the local composition of a clot

(local-scale), and the other category that reveals the extent of concordance between a number of local scale measurements made from the CSGS and the histological characterization by the Core Laboratory (Core Lab) of the full clot retrieved during the EVT procedure (clot scale).

The **tertiary objective** of the study is to explore possible relationships between CSGS measurements and intervention parameters such as first pass effect, number of passes to successfully retrieve the clot and other key parameters. Due to the nature of the tertiary objectives, not all centers may contribute to the data collection.

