### c) Secondary Endpoints

There are 7 secondary endpoints. The secondary endpoints are all performance endpoints and include:

1. The concordance between occlusion measurement done by CSGS, and the histopathology results of the clot retrieved during the EVT procedure, at the level of red blood cell content in the occlusion (clot scale).  
To determine the histopathological results of the clot, the mean will be taken of the percentage RBC composition of the 3 analyzed slices (value between 0 and 1) provided by the Core Lab.  
Significant correlation will be judged at the 0.05 significance level by the t-statistic of the relation between RBC content as output by the prediction model and the RBC content as quantified by the MSB-staining histological analysis
2. The ability of CSGS detecting the proximal end of the occlusion (sensor-scale), as compared to the physician's labelling (tag 'PRE-CLOT' for no occlusion contact) and tag 'CLOT' for occlusion contact). The concordance will be judged by the Area Under the Receiver Operator Characteristic curve on the validation set. The same methodology will be used as for the primary performance endpoint. Data from the interventions in the development and validation sets will be the same as for the primary endpoint.
3. Procedural success defined as the ability to navigate CSGS to the occlusion and measure electrophysiological properties of the occlusion. Procedural success is achieved from the moment that at least 1 effective measurement is captured by the CSGS in or beyond the clot.
4. The ability to perform binary classification of individual electrophysiological parameter measurements (local scale) by distinguishing local regions with substantial platelet content (platelet-positive) from regions with negligible platelet content (platelet-negative) in the occlusion. The ability to perform binary classification will be evaluated by the performance metric area under the ROC curve computed from the platelet-content score predicted on the validation set. The same methodology will be used as for the primary performance endpoint.
5. The concordance between aggregated occlusion measurements (clot scale) done by CSGS, and the histopathology results of the clot retrieved during the EVT procedure, regarding platelet content in the occlusion.  
To determine the histopathological results of the clot, the platelet composition (value between 0 and 1) will be averaged over the 3 analyzed slides provided by the Core Laboratory.  

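### SAP 4.c item 3 grants procedural success for a reading beyond the clot, so the rate can exceed what the endpoint definition and the protocol would count

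*SAP*

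**What the plan says.** SAP 4.c item 3 has two sentences. The first is the definition: "Procedural success defined as the ability to navigate CSGS to the occlusion and measure electrophysiological properties of the occlusion". The second is the operative rule: "Procedural success is achieved from the moment that at least 1 effective measurement is captured by the CSGS in or beyond the clot".

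The protocol defines the endpoint in section 11.2 item 3 as "defined as the ability to navigate CSGS to the occlusion site and measure electrophysiological properties of the occlusion". Its operative rule in section 15.4.2 item 3 is "Procedural success is achieved from the moment that at least 1 evaluable measurement is captured by the CSGS". Section 15.2 supplies the meaning of evaluable: "An evaluable acquisition is defined as a 'CLOT tag' or 'Clot or beyond' tag with non-anomalous (see criteria section 15.6) impedance measurement".

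The secondary objective (protocol 10.2, repeated in SAP 2) equates performance with "the feasibility to measure electrophysiological properties of the occlusion in vivo during EVT procedures".

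Protocol 13.8 plans up to six readings per patient. Two or three lie inside the occlusion, and the last is described as "1 measurement at the most distal advancement of the guidewire (ideally distal to the occlusion".

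Neither document states a denominator or a target rate for procedural success.

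**The concern.** The definition asks for two things: the wire reaches the occlusion, and the occlusion is measured. The SAP's operative rule can be met with only the first. Suppose the in-clot readings were never tagged, or were taken while the microcatheter covered the sensor, and the most distal reading was valid. That patient is a success under the SAP although nothing about the clot was recorded. Both failure routes are named in protocol 15.6 and SAP 8.c.vi.

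What is at stake is a main feasibility figure of a first-in-human study. The rule would answer whether the wire could pass the clot and return a signal, which is a different question from whether it could measure the clot. The same patient could also succeed under the SAP and fail under the protocol, although the SAP change history says that version 2 was written to align with version 6 of the protocol.

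**Working it through.** **1. The conditions side by side.** Each row shows whether one valid reading under the given tag is enough.

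| Rule | CLOT tag | Clot or beyond tag | MOST DISTAL tag, past the clot |
|---|---|---|---|
| Endpoint definition (SAP 4.c item 3, first sentence; protocol 11.2 item 3) | yes | only if in the clot | no |
| Protocol 15.4.2 item 3 with 15.2 | yes | yes, wherever it lies | not listed |
| SAP 4.c item 3, second sentence | yes | yes, wherever it lies | yes |
| SAP 8.b, Local-Scale Performance Population | yes, if experts place it in the clot | only if experts place it in the clot | no |

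The SAP rule is the loosest row. The protocol differs from the endpoint definition only in the middle column.

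**2. Do the documents treat a beyond-clot reading as a measurement of the clot?** They do not. SAP 4.b reserves the clot-scale term for readings in contact with the clot. In SAP 4.d item 2, experts label the CLOT, Clot or beyond and MOST DISTAL acquisitions as contact or no contact, and the first non-contact reading serves as the negative example. SAP 6 requires clot contact for the development set.

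**3. Direction.** Let I be the patients with at least one valid in-clot reading and B those with at least one valid beyond-clot reading. The SAP counts I ∪ B and the definition counts I. The difference is the number of patients in B but not in I, which is zero or positive. The rate can only be equal or higher.

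**4. Size.** The plan gives no figure for this endpoint. Its only relevant number is the total sample size, which reproduces: (11 + 14)/0.60 = 41.67, rounded up to 42. That figure serves the primary performance endpoint and is not affected here.

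With k beyond-only patients among n in the denominator, the excess is k/n. Both k and n are assumptions.

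- n = 42: k = 0 gives 0; k = 1 gives 1/42 = 2.4 points; k = 2 gives 4.8; k = 5 gives 11.9.
- n = 31 (the treated subjects mentioned in protocol 15.6): k = 1 gives 1/31 = 3.2 points.

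**5. What the documents suggest about k.** Protocol 15.5 reports an average of 3 tagged acquisitions with clot contact in the first 9 procedural successes, so 9 × 3 = 27 in all. If a patient can have at most 3 (the readings planned inside the occlusion), 27/3 = 9, and no patient had none. If the most distal reading may also be in contact, the maximum is 4. Then 27/4 = 6.75, so at least 7 patients had contact and at most 2 had none. The average may be rounded, and the success rule applied to those 9 is not stated.

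**The case against.** The strongest reply is that the SAP phrase loosely renders the Clot or beyond tag, since the SAP was revised to match the protocol. On that reading the gap shrinks to one tag of uncertain position. This is possible, but the sentence names no tag, uses an undefined word where the protocol uses a defined one, and as written covers any reading past the clot.

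A second reply is that a wire beyond the clot must have touched it. Passing is not measuring, and if crossing were enough the second half of the definition would be redundant.

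Third, beyond-only patients may be rare. The first 9 successes point that way, and that stands. A reader might infer that feasibility *is* overstated; the documents support only that it *can* be. Nor can 25/42 (59.5%) serve as the true in-clot rate. The 25 is the planned number of interventions with an evaluable measurement, and evaluable already includes the Clot or beyond tag.

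Fourth, the failures are not hidden altogether. Malfunction rates, device deficiencies and a listing of each patient's analysis sets are planned. Connection loss is also a weak example, because it would often remove the later distal reading too. Both points stand.

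A reader might also infer that a beyond-only patient is useless for every performance endpoint. SAP 4.d does not support this: distal-end detection uses non-contact readings, wall labelling includes MOST DISTAL acquisitions, and prediction of the number of passes may draw on all readings.

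**Conclusion.** The point holds as a contradiction inside SAP 4.c item 3 and a mismatch with the protocol. The rule as written can count a patient whose occlusion was never measured. Any effect is upward. Its size is unknown and may be zero; each beyond-only patient is worth about 2.4 points if 42 treated patients form the denominator.

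It would be wrong to say that the protocol has the same gap. The protocol admits the Clot or beyond tag without establishing contact, but its list of evaluable acquisitions does not include MOST DISTAL readings.

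Procedural success is descriptive, with no threshold. Neither the sample size nor a primary endpoint depends on it. The rule should be corrected because it departs from its own definition and the correction is cheap.

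**What to change.** Use one definition in SAP 4.c item 3 and protocol 15.4.2 item 3: at least one non-anomalous acquisition (criteria of protocol 15.6) with clot contact. Clot contact means a CLOT tag, or a Clot or beyond tag that the expert labelling planned in SAP 4.d item 2 and SAP 8.b places in contact. Delete *or beyond* from the SAP criterion and replace *effective* by this term.

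Apply the definition to all treated patients and state that denominator. The Local-Scale Performance Population excludes development patients, so its contact criterion has to be extended to them.

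Report patients with only a beyond-clot reading on a separate line, for example as crossed but occlusion not measured. The broader count can then be recovered by addition.

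The cost is a short change to both documents, which the SAP allows because it is to be finalised before database lock (SAP 1), plus contact labels for the Clot or beyond acquisitions of development patients where these are lacking. There are two downsides. The reported rate may be slightly lower, and for uncertain-position tags the count will rest on the judgement of sponsor experts and no longer on the operator's tag alone.

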#### d) Tertiary Endpoints

There are 6 tertiary more exploratory endpoints. The tertiary endpoints assess the correlation between the CSGS measurements with intervention parameters such as:

1. Arterial wall detection for individual measurement - The local detection of arterial wall vs. clot when clot-contact is ensured. Differentiation of the arterial wall cannot be validated by external means. Expert labelling will be done on tagged acquisitions (PRE CLOT, CLOT, CLOT or beyond, MOST DISTAL): for each electrode pair the expert will evaluate whether it is in contact with arterial wall or not. Comparison with the prediction model will be made at such local-scale (single electrode pair) by using the same performance metric as for the primary endpoint, i.e. by means of the AUC of ROC.
2. The ability of CSGS detecting the distal end of the occlusion. Two comparisons will be made: one with expert labelling on tagged acquisitions and one compared to external evaluation when distal injection of contrast agent allowed the core lab to evaluate the positioning. The expert will label the CLOT, CLOT or beyond, and MOST DISTAL tagged acquisitions as whether the sensor is in clot contact or not. The last clot contact will be used as the positive example and the first labelled non-contact measurement will be used as the negative example. Regarding the subset of interventions for which a distal injection of contrast agent allowed the identification of the location of the sensor in or behind the clot by the imaging core lab, the ground truth will be used identically on the last tagged acquisition in the clot and the first tagged acquisition where the sensor is established behind the clot. The AUC of ROC will be used identically that for the Secondary endpoint for the proximal detection. Data from the interventions in the development and validation sets will be the same as for the primary endpoint.
3. The number of passes - The prediction of the number of passes to remove the clot. Interventions with successful clot retrieval are used. The input may include all the electrophysiological measurements of the intervention. The output is the number of passes needed to remove the clot as reported by the investigator. Data from the interventions in the development and validation sets will be the same as for the primary endpoint.
4. The prediction of first pass effect. Interventions can be split into two groups whether or not a single pass was enough to achieve a TICl score better than 2b; this forms the positive and negative groups respectively. The prediction can be evaluated with a ROC curve and the AUC metric, as described for the Primary endpoint, but where the prediction is made at the intervention level. The same methodology will be used as for the primary performance endpoint. Data from the interventions in the development and validation sets will be the same as for the primary endpoint.
5. The prediction of the etiology of the clot. Data from the interventions in the development and validation sets will be the same as for the primary endpoint.
6. The prediction of the type of device that has better chances to remove the clot. Data from the interventions in the development and validation sets will be the same as for the primary endpoint.

